3. OBJECTIVES

3.2 Primary Objective

To estimate the proportion of MDR TB amongst new and previously treated TB cases.

- 3.3 Secondary Objective
 - To evaluate accuracy of clinical diagnosis by comparing clinically defined TB

to laboratory confirmed TB.

- To compare AFB and Xpert MTB/RIF as TB diagnostic tests against culture result.
- To estimate the sensitivity and specificity of Xpert MTB/RIF in detecting Rif susceptibility against Drug Susceptibility Test (DST).
- To estimate the proportion of cured, completed, failed, died and lost to follow up as treatment outcomes in drug susceptible TB (DS-TB) cases and drug resistant TB (DR-TB) cases.
- To evaluate the association of treatment success (cured or completed) with the following data:
 - 1. Demographics (age, sex)
 - 2. TB contact history
 - 3. Smoking habit
 - 4. Treatment seeking behavior
 - 5. Co-morbidities (HIV, DM, cancer)
 - 6. Primary and secondary drug resistance
 - 7. Symptoms
 - 8. Cavitary disease
 - 9. Nutritional status
 - 10. Treatment regimens
 - 11. Patient reported compliance
 - 12. Numbers of bacteria by AFB test
 - 13. TB strains (e.g., Beijing)

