4.4 Population and Sample Size

This is a descriptive study with the goal of estimating rates MDR in two separate cohorts (new and previously treated TB cases). WHO global report in 2013 estimated 1.9% MDR TB cases in new TB cases and 12% MDR TB cases in previously treated TB cases for Indonesia. This study will analyze 250 bacteriologically confirmed new TB participants and 250 bacteriologically confirmed previously treated participants. We estimate that 25% of presumptive new TB participants who satisfy study entry criteria will be bacteriologically confirmed TB. Similarly, we estimate that 70% of previously treated cases will be bacteriologically confirmed TB. Therefore, to obtain 500 bacteriologically confirmed TB cases and 357 presumptive previously treated cases will be enrolled, for a total of 1,357 enrolled. The proportion of confirmed TB cases amongst new and previously treated cases is an estimation and will be re-evaluated during the course of the study. Refer to the interim analysis section below for details.

Table 4.4.1 describes the expected precision (confidence bounds and width) for observed proportion of MDR amongst previously treated cases. With 250 participants and an observed MDR proportion of 12%, the confidence interval will be (0.085, 0.162). The precision of the estimated proportion of MDR does not improve considerably when increasing the sample size to 300. The confidence interval for a sample size of 300 with an MDR proportion of 12% is (0.085, 0.162), while decreasing the sample size to 200 has a more striking impact on the bounds increasing the lower bound to 0.078 and the upper bound to 0.173.

When considering the sample size for new TB cases, we note that the precision of binomial confidence intervals based on exact Clopper Pearson method increases as the proportion gets closer to zero. As a result, we find the true MDR rate is more precisely estimated with a sample size of 250 for new TB cases (compared to previously treated cases, where the MDR rate is expected to be around 12%). With a sample size of 250

new TB cases, the expected 95% confidence interval is (0.007, 0.046). (Table 4.4.1) Exact Clopper Pearson binomial confidence interval method formula:

$$\left(1 + \frac{n - x + 1}{xF\left[1 - \frac{1}{2}\alpha; 2x, 2(n - x + 1)\right]}\right)^{-1} < \theta < \left(1 + \frac{n - x}{[x + 1]F\left[\frac{\alpha}{2}; 2(x + 1), 2(n - x)\right]}\right)^{-1}$$

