4.6 Instruments and Data Collection'

The following instruments and data collection methods will be used in this study. Further information may be found in protocol sections 4.6.2-4.6.5.

- 4.6.1 Instruments:
 - a. Forms
 - i. Informed consent
 - ii. Source documents
 - iii. Case report forms (CRFs)
 - iv. Screening Log
 - v. Enrollment Log
 - b. Databases
 - i. OpenClinica

ii. INA-RESPOND specimen database

- c. INA-RESPOND portal
- 4.6.2 Eligibility determination and enrollment:

Enrollment and baseline visit (visit 1)

Potential participants will be referred by physicians at participating hospitals.

Following referral, research assistant will check the eligibility criteria. Thus, the potential participant will be offered information on the study. If the patient agrees, he/she will sign the informed consent document and will be considered enrolled in the study. All baseline procedures should be done in five working days, although the result may come later. Enrollment day is considered as Day 0.

Demography, clinical data, and physical examination results including body weight and height will be obtained. The initial data collection will take time about 30-60 minutes.

Participant should bring enough sputum that can be considered eligible for AFB, Xpert MTB/RIF, and culture examination. Sputum induction by inhalation medicine will be considered for participants that have difficulty to produce sputum according to site SoC. The remaining sputum will be stored for TB related future testing. Participant who cannot provide enough sputum for those examinations will be considered as end of study and stop following the study procedures.

20 cc blood will be drawn for assessment of comorbidities (HIV test and HbA1c), for other examinations needed either for study or for SoC. Such as Hb, ureum, creatinine, AST, and ALT. Left over specimen will be used for future TB related examinations and repository. Less blood volume because unanticipated problem related to blood draw such as collapsing vein would not be considered as protocol deviation. 10 cc of urine will also be collected and stored for future TB related tests. Saliva will also be collected for storage.

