4.7.2 Analysis

This is an observational study to describe rates of MDR TB amongst new and previously treated TB cases in Indonesia. Risk factors for MDR will be evaluated as a secondary objective. Additional secondary objectives include a description of treatment outcomes (cure, failure, death, completed treatment) and evaluation of associated risk factors for poor outcome, comparison of diagnostic accuracy of AFB and Xpert MTB/RIF (relative to culture) and an estimation of Xpert MTB/RIF Rif susceptibility testing sensitivity and specificity relative to standard DST. Research objectives will be analyzed as described below.

Primary objective

 To estimate the rate of MDR-TB amongst new and retreated TB cases. Proportions of MDR will be estimated, along with exact 95% confidence intervals based on a binomial distribution. Case definitions of MDR, new and previously treated TB are provided in Appendix B.

Secondary objective

- To estimate treatment outcomes (cured, failed, died, treatment completion, and lost to follow up) according to susceptibility pattern. Proportions of participants within each category will be estimated along with confidence intervals. Definitions of treatment outcomes are provided in appendix B.
- 2) To evaluate risk/protective factors for treatment success (cured or completed treatment vs failed or died or loss to follow up). These factors include: demographics (age, sex), TB contact history, smoking habit, treatment seeking behavior, co-morbidities (HIV, DM), primary drug resistance, symptoms, no cavity in the lung, nutritional status, treatment regimens, compliance, numbers of bacteria and TB strains (e.g., Beijing). Logistic regression models will be used to describe associations of treatment success with these factors.
- 3) To evaluate risk/protective factors for treatment interruption (loss to follow up vs other treatment outcome). These factors include: demographics (age, sex), TB contact history, smoking habit, treatment seeking behavior, co-morbidities (HIV, DM, and other comorbidities), primary drug resistance, symptoms, cavity in the lung, nutritional status, treatment regimens, compliance, numbers of bacteria and TB strains (e.g., Beijing). Logistic regression models will be used to evaluate associations of treatment interruption with these risk factors.
- To compare clinically defined TB against laboratory confirmed TB. Accuracy will be estimated along with 97.5% confidence intervals.

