- 5) To compare the sensitivity and specificity of AFB and Xpert MTB/RIF relative

to culture result. Sensitivity and specificity will be estimated along with 97.5% confidence intervals. McNemar's statistic will test whether the sensitivity and specificity differ between AFB and Xpert MTB/RIF.

6) To estimate sensitivity and specificity of Rif susceptibility results in Xpert MTB/RIF against result in DST as gold standard along with 97.5% confidence intervals.

More specific plans for these analyses will be developed prior to the start of enrollment, and the plans may be adjusted during the course of the study.

Interim Analyses

Amongst presumptive new TB cases, we estimate that 25% will have confirmed TB, while amongst presumptive previously treated cases, we estimate that 70% will have confirmed TB. In order to ensure adequate numbers of TB cases, the accuracy of these estimates will be evaluated at 6 and 12 months after the study commences. Because of the expected two months waiting period for culture results, earlier looks at the data may not be informative.

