Failed	Attending TB team report	 Treatment terminated or need for permanent regimen change at least two anti-TB drugs because of: Lack of conversion at the end of intensive phase; or Bacteriologocial reversion in the continuation phase after conversion to negative; or Evidence of additional acquired resistance to fluoroquinolones or second-line injectable drugs; or Adverse drug reactions
Died	Attending TB team report	Died for any reason during course of treatment
Loss to follow up	Attending TB team report	Treatment was interrupted for two consecutive months or more.
Not evaluated	Attending TB team report	No treatment outcome is assigned. This include cases 'transferred out' to another treatment unit as well as cases for whom the treatment outcome is unknown.
Treatment success	Attending TB team report	The sum of Cured and completed treatment.

Demographics						
Age	Patient report	Last birthday				
Sex	Patient report	male and female				
Patient's history						
TB close contact	Patient report	Living in a same house with person who has TB				
Smoking habit	Patient report	Smoking status of participants				
Treatment seeking behavior	Patient report	History of health facility that been visited for treating these TB symptoms				
Co Morbidities						
HIV	Clinical and laboratory evaluation support HIV evidence	Positive result of HIV test				
Diabetes mellitus	Clinical and laboratory evaluation support diabetes evidence glucose test according to site SoC	Positive result of diabetes				
Symptoms	Patient report	Presence of TB symptoms from previous visit to current visit				
Nutritional status	BMI calculation based on data of Height and weight	< 18.5				
Treatment regiment	Source documents	Regiment of anti TB drugs given to the patients according to SoC				
Compliance	Patient report or blister count	Percentage of scheduled medication minus any medication left in the blister or based on patient report				

REFERENCES

1. World Health Organization W. Global Tuberculosis Control, Surveillance, Planning and Financing. Geneve: 2006.

2. World Health Organization W. Global Tuberculosis Control 2010. Geneve: 2010.

3. World Health Organization W. Global Tuberculosis Report 2016. Geneva: World Health Organization; 2016.

4. Departemen Kesehatan Republik Indonesia. Pedoman Nasional Penanggulangan Tuberkulosis. Jakarta2007.

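### Nutritional status is defined only as BMI below 18.5, so the risk-factor models would by default use a yes/no BMI term although continuous baseline BMI is available

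*Combined protocol and SAP*

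**What the plan says.** Section 3.3 lists "Nutritional status" among the factors to be related to treatment success. Section 4.7.2, item 2, gives the method: "Logistic regression models will be used to describe associations of treatment success with these factors". Item 3 uses the same kind of model for treatment interruption and also lists nutritional status.

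The variable is defined in Appendix B. The measurement is "BMI calculation based on data of Height and weight" and the operational definition is a BMI below 18.5, with no other category or scale. In the same table, age and compliance are described on numeric scales.

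The measurements are taken for everyone at entry. Section 4.6.2 says that "physical examination results including body weight and height will be obtained" at the baseline visit, and Appendix A schedules both then, with weight repeated through follow-up.

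Section 4.7.2 does not state the functional form of any factor. It adds: "More specific plans for these analyses will be developed prior to the start of enrollment". Those plans are not part of the documents.

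**The concern.** A one-cut definition turns a continuous measurement into a yes/no variable. A BMI of 18.4 and one of 18.6 fall on opposite sides, while 18.6 and 30 are treated as the same. If the relation between BMI and outcome is smooth, this discards information and lowers the power to detect or describe the nutrition association. Continuous BMI needs no new data.

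**Working it through.** The documents give no power or precision figure for nutritional status, so there is nothing of theirs to reproduce on this point.

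**Inputs from the documents.** Cut: BMI below 18.5 (Appendix B). Scale of the analysis: "This study will analyze 250 bacteriologically confirmed new TB participants and 250 bacteriologically confirmed previously treated participants" (Section 4.4), so 250 + 250 = 500. This is used for scale only; the number entering each logistic model may differ.

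**Assumptions, not in the documents.** Share q below 18.5; normal BMI; linear effect on the log odds; 20% non-success; log odds ratio 0.35 per SD (odds ratio about 1.42).

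**Step 1: information kept by the split.** For a normal covariate with a linear effect, relative efficiency is E = φ(z_q)² / [q(1 − q)], where φ is the standard normal density and z_q its q-quantile.

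| q below cut | φ(z_q)² | q(1 − q) | E | Loss | 500 × E |
|---|---|---|---|---|---|
| 0.50 | 0.1592 | 0.25 | 0.637 | 36% | 318 |
| 0.30 | 0.1209 | 0.21 | 0.576 | 42% | 288 |
| 0.20 | 0.0784 | 0.16 | 0.490 | 51% | 245 |
| 0.10 | 0.0308 | 0.09 | 0.342 | 66% | 171 |

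The formula is symmetric, so 70% below gives the same loss as 30% below. Under this model 36% is the smallest loss that any single cut can give, and 42% is not an upper limit. With a lognormal BMI (coefficient of variation 0.15 or 0.20) and q from 0.30 to 0.70, the loss is about 37% to 50%.

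**Step 2: approximate power by hand.** The noncentrality for a linear term is 500 × 0.20 × 0.80 × 0.35² = 9.8.

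- Linear, 1 df: Φ(√9.8 − 1.96) = Φ(1.17), about 88%.
- 3-knot spline, 2 df, same noncentrality: about 81%.
- Split, q = 0.50: 9.8 × 0.637 = 6.24; Φ(2.50 − 1.96), about 70%.
- Split, q = 0.30: 9.8 × 0.576 = 5.64; Φ(2.38 − 1.96), about 66%.

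**Step 3: simulation of the same case.** Repeated sets of simulated studies, tested at 5%, with q from 0.30 to 0.50, gave about 86% to 89% for linear BMI, 80% to 82% for the 3-knot spline and 66% to 70% for the split. At q = 0.20 the figures were about 86%, 79% and 62%. The hand calculation and the simulations agree for q from 0.30 to 0.50.

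**Step 4: a different true shape.** With a true step at the cut (log odds ratio 0.7, q from 0.30 to 0.50), the split had about 83% to 88% power and the spline about 56% to 63%. The ranking reverses.

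**The case against.** The strongest reply is that the plan never says a binary BMI goes into the models. Appendix B is a table of definitions, not a model specification; its age entry does not fix a functional form either. The cut may be only a descriptive label for undernutrition, and Section 4.7.2 defers detail to later plans. This stands in part. A reader might infer that the protocol commits to the split or throws data away; it does neither, and raw height and weight are retained. But the cut is the only definition given, and the deferral does not replace it, so the binary term is what follows from the text.

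The second reply is that the gain depends on an assumed shape. This also stands: Step 4 shows that a step at 18.5 would favour the split. The documents neither suggest nor rule out such a step, which is a reason to keep the category as a secondary analysis.

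Third, part of the advantage of a linear term is lost if a spline is used. Against the split, the spline gains roughly 10 to 15 points in the illustrative case with 30% to 50% below the cut, not the larger difference shown by the linear term.

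**Conclusion.** The point holds as a minor improvement to secondary analyses. As written, the protocol leads to a yes/no BMI term in the models of items 2 and 3 when a continuous one is available at no cost. For a roughly linear effect and a normal BMI, the loss is 36% at best, 42% with 30% below the cut and 51% with 20% below.

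Two stronger readings are not supported. One is that this study will lose a fixed 36% to 42% of the information: that needs a share below 18.5 between about 30% and 70%, a normal BMI and a linear effect, and the documents give none of these. The other is that the split will leave material residual confounding in the other associations. That is possible in principle, but the documents name no exposure for which BMI is a designated confounder and give nothing from which to size it.

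The primary MDR proportions are untouched.

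**What to change.** Add one sentence to the analysis plan: in the models of Section 4.7.2, items 2 and 3, baseline BMI enters as a pre-specified continuous term, either linear or, if curvature is to be allowed, a restricted cubic spline with 3 knots. Choose between the two before looking at outcomes. Say that it is baseline BMI, since weight is also recorded at later visits. Keep the below-18.5 category for the descriptive table and as a secondary analysis, which also covers a possible step at that value.

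No new data are needed. The downside is a less simple effect display and, for the spline, one extra degree of freedom, which costs about 7 points of power against a linear term when the effect really is linear (88% − 81% in Step 2).

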After the sputum culture shows positive results of M.*tuberculosis*, the *M.tuberculosis* isolate will be tested for DST and also be stored. New TB cases with Rif susceptible Xpert MTB/RIF result will be tested for first line DST, continue by second line if first line DST result shows drug resistant TB. New TB cases with Rif resistant Xpert MTB/RIF will be directly tested for first and second line DST. Previously treated TB cases will be directly tested for first and second line DST.

DS-TB participants who decide to take the TB treatment in puskesmas (primary health care) may not come to visit(s) except for study visit which the study gives compensation for participant's attendance. So that for those participants, study will provide a record, named "TRIPOD Diary", to be completed on each visit at Puskesmas. The TB program manager or designee at the Puskesmas will give their signed as a verification of this record. TRIPOD Diary will be mentioned further in MOP.

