4.6.3 Ongoing monitoring and evaluation

During treatment, participants will be seen every month for 6 months and then every 2 months until end of treatment or **maximum at month 24**th. Then participants also will be assessed 6 months after end of treatment. In general, participants will have between 1 to 16 numbers of follow up visits. Study will also record the data of several participants who may need month 7 and/or month 8 and/or month 9 visits, **for example participant receiving category 2 treatment, participant with diabetes comorbid.** Study visits will occur at the same time as clinical visit. If the participant does not come for a clinical visit it will not be considered a deviation from the protocol.

Except 6 months post treatment visit, every study visit will collect data on each comorbidity include HIV, diabetes, and cancer. Study will also collect data on weight, TB symptoms, TB treatment compliance, sputum examination results (if available), and treatment regimen. Participants' compliance will be measured by counting how many medications still left in the blister pack (if available) or based on participant report if the patient does not bring the blister. TRIPOD diary will assist the research assistant to measure participant compliance who is taking the medication in the primary health care/puskesmas.

All participants will have follow up for treatment of TB and routine testing as mandated by the National Guidelines and provided by the hospital in accordance with Appendix A. Additional AFB tests on month 1, culture test on month 1 and 2, and chest x-ray at the end of treatment visit, will be conducted for all drug susceptible participants.

Sputum induction by inhalation medicine will be offered to participants that have difficulty to produce sputum.

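### On the blister-count route, compliance has no term for doses collected, so a participant who skips a supply for under two months and then brings an empty blister can score 100%

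*Combined protocol and SAP*

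**What the plan says.** Appendix B (Operational Definition, Compliance) gives the measure as "Percentage of scheduled medication minus any medication left in the blister or based on patient report". Its measurement column allows either patient report or a blister count.

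Section 4.6.3 describes the operation as "counting how many medications still left in the blister pack (if available"), or "based on participant report if the patient does not bring the blister". For participants who take their drugs at primary health care it adds that the "TRIPOD diary will assist the research assistant to measure participant compliance". Section 4.6.2 has that diary filled in at each puskesmas visit and verified by the TB programme manager there or a designee, with further detail left to the MOP.

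On timing, section 4.6.3 says "participants will be seen every month for 6 months and then every 2 months until end of treatment" or month 24 at the latest. Section 4.5.3 ends participation at an interruption of two months or more, and Appendix B classes an interruption of two consecutive months or more as loss to follow-up.

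Section 4.7.2 lists compliance among the factors for treatment success and again for treatment interruption. For the first it states: "Logistic regression models will be used to describe associations of treatment success with these factors". The second is also to be analysed by logistic regression.

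**The concern.** A count of leftover pills measures intake only if everything scheduled was first collected. The definition subtracts what remains in the pack from what was scheduled, and never asks what was handed out. A participant with no drug for several weeks who finishes the packs that were collected brings nothing to subtract.

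The error is more than noise around the right value, because it can reverse the order of two participants. One who collects every supply and openly returns a few pills scores below one who went a month without drug. Compliance is a covariate in two planned models, so this ordering is what those models would use. Gaps shorter than two months matter most here, because nothing else in the plan classifies them.

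**Working it through.** The documents state no numerical compliance figure, so there is none to reproduce. The check applies the written rule to simple cases.

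**Symbols.** S = doses scheduled, D = doses collected, L = doses left in the blister.

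**Assumptions not in the documents.** One dose a day and 30 doses per supply. This gives S = 180 over six months and S = 720 over 24 months. Two months is taken as 60 days, so the longest gap that escapes the interruption rule is 59 days.

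**Formulas.**
- As written, blister route: A = 100 × (S − L) / S
- Actual intake, if every collected dose not returned was taken: B = 100 × (D − L) / S
- As written, but reading scheduled as dispensed: C = 100 × (D − L) / D

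Subtracting, A − B = 100 × (S − D) / S. The overstatement is exactly the share of scheduled doses never collected. It is zero only when D = S.

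| Case | S | D | L | A | B | C |
|---|---|---|---|---|---|---|
| One interval, all collected, 6 left | 30 | 30 | 6 | 80.0% | 80.0% | 80.0% |
| Two intervals, one supply skipped, none left | 60 | 30 | 0 | 100% | 50.0% | 100% |
| Six months, one supply skipped, none left | 180 | 150 | 0 | 100% | 83.3% | 100% |
| Six months, 59 days not collected, none left | 180 | 121 | 0 | 100% | 67.2% | 100% |
| Six months, all collected, 10 left | 180 | 180 | 10 | 94.4% | 94.4% | 94.4% |
| Six months, all collected, 30 left | 180 | 180 | 30 | 83.3% | 83.3% | 83.3% |
| 24 months, one supply skipped, none left | 720 | 690 | 0 | 100% | 95.8% | 100% |

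**What the table shows.**
1. When everything is collected, all three versions agree. The written rule fails only when a supply is skipped.
2. Row 3 against row 5: (180 − 0)/180 = 100% for a participant who took 150 of 180 doses, and (180 − 10)/180 = 94.4% for one who took 170. The order is reversed.
3. Row 3 against row 6: both took 150 of 180 doses (83.3%), but one scores 100% and the other 83.3%.
4. Reading scheduled as dispensed (column C) does not help. The skipped period drops out of numerator and denominator, and the score is still 100%.
5. The same skipped supply costs 50.0 points over two intervals, 16.7 over six months and 4.2 over 24 months. The interval therefore has to be stated, and neither Appendix B nor section 4.6.3 states it.

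**The case against.** The strongest reply is that the blister count is only half of the definition. Where no blister is brought, section 4.6.3 falls back on participant report, and section 3.3 itself names the factor as compliance reported by the patient. A supply that was never collected has no blister, so for that interval the participant might simply be asked. For those treated at a puskesmas there is also a verified diary. The documents do not say whether an interval with a missed visit is scored or left missing, and section 4.7.2 promises more specific analysis plans.

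Much of this stands, and it limits the point to the blister-count route. It does not remove it. A participant who skipped one supply and later brings an empty pack from another does have a blister, so section 4.6.3 directs the count. Nothing lets report or diary override that count, and the diary is said only to assist.

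Two stronger readings are tempting, but the documents do not support them.

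- **That the plan expects missed supplies.** A reader might infer this from "If the participant does not come for a clinical visit it will not be considered a deviation from the protocol", or from the statement that drug-susceptible participants at a puskesmas "may not come to visit(s) except for study visit which the study gives compensation for participant's attendance". Both concern attendance at study or clinical visits. The puskesmas group may stay away precisely because they take their treatment elsewhere, and a missed visit is not a missed supply.
- **That the association is biased toward none by a known amount.** Any odds ratio or power figure would need a non-collection rate, a distribution of missed doses and an effect size. The documents give none of these.

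**Conclusion.** The point holds for the blister-count route. As written, the rule equals intake only when every scheduled dose was collected. For a gap shorter than two months followed by an empty blister, it overstates compliance by the uncollected share of the schedule. Under the assumed 180 daily doses that is 16.7 points for one skipped 30-dose supply (100% against 83.3%), and 32.8 points at the 59-day limit (100% against 67.2%). The result needs only the algebra; the sizes rest on the assumed dose count and supply size.

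The effect on the two logistic models is unknown, because the documents give no rate of non-collection. Misclassification of this kind is likely to dilute the association, but the direction is not guaranteed. Loss to follow-up counts as a non-success in section 4.7.2, so the scoring error may depend on the outcome.

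Only secondary analyses are touched. The primary MDR proportions do not use compliance. The plan should still be changed, because a stated rule gives a wrong score and a better one is cheap.

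**What to change.** In Appendix B and section 4.6.3, define compliance as

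100 × (doses collected or supervised − doses left) / doses scheduled

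over an interval that is stated, and count scheduled doses not collected in that interval as not taken.

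Set the order of sources:
1. Doses collected come from the treatment or dispensing record, or from the signed TRIPOD Diary for puskesmas participants.
2. Doses left come from the blister count.
3. Participant report is used only where neither a record nor a blister is available.
4. The source used is flagged for each value, so that the models can be repeated by source.

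State also whether an interval with a missed visit is scored from the record or left missing.

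The cost is one CRF field for doses collected since the last visit, with some extra transcription. Some participants will have no dispensing record, and their values will still rest on report. The change concerns measurement only and leaves treatment and visit schedules as they are.
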